## **10.7. Provision of Study Results to Investigators, Posting of Information on Publicly Available Clinical Trials Registers and Publication**

- Where required by applicable regulatory requirements, an investigator signatory will be identified for the approval of the clinical study report. The investigator will be provided reasonable access to statistical tables, figures, and relevant reports and will have the opportunity to review the complete study results at a GSK site or other mutually-agreeable location.
- GSK will also provide the investigator with the full summary of the study results. The investigator is encouraged to share the summary results with the study subjects, as appropriate.
- GSK will provide the investigator with the randomization codes for their site only after completion of the full statistical analysis.
- The procedures and timing for public disclosure of the results summary and for development of a manuscript for publication will be in accordance with GSK Policy.

## **10.8. Review Committees**

### **10.8.1. Data Review Committee (DRC)**

- A DRC will be utilised in this study to ensure objective medical and/or statistical review of efficacy and/or safety issues in order to protect the ethical and safety interests of subjects and to protect the scientific validity of the study via review of unblinded study data.
- The DRC (consisting of external rheumatology, infectious disease and respiratory experts, and GSK study team members that have no involvement in the acquisition of the data or direct contact with sites) will review ongoing unblinded safety data from the study and unblinded efficacy data at the interim analyses. The first DRC review of safety data will be conducted after approximately 10 subjects per arm have completed 5 weeks of treatment, and subsequent reviews will take place

approximately every 12 weeks thereafter until the end of the study. The decision to stop the study or randomisation to specific arms will be made by the DRC.

- The DRC members will review unblinded summary safety data, and if required will review anonymised individual data on request. Only the DRC statistician will be unblinded to individual subject treatment allocations.
- At the defined interim analysis time points the DRC will also review unblinded efficacy data. Unblinded efficacy data will also be reviewed if needed outside of the planned interim analyses to assess benefit:risk based on the safety findings. When possible, these reviews will be scheduled to align with planned safety reviews. The schedule of planned interim analyses and the analysis plan for DRC reviews will be described in the relevant guidance documents that will be approved prior to the first analysis, which will be available upon request.
- The DRC will remain in place for review of emerging unblinded safety data until all subjects have completed the safety follow-up visit (*i.e.*, 12 weeks after the last dose of study medication, Week 62 visit). The Week 24 efficacy and safety analyses (primary analysis) will be made available to the study team more broadly and to regulatory authorities as these data will support future clinical development plans.
- A vote of the DRC committee will be taken at the conclusion of each meeting of the DRC. Each meeting of the committee will be associated with an active recommendation of proceeding unchanged, modifying or terminating the study. Further details will be outlined in the DRC Charter.

## 12. APPENDICES

### 12.1. Appendix 12.1 - Abbreviations and Trademarks

°C	Degree Celsius
µg	Microgram
ACPA	Anti-cyclic citrullinated protein antibody
ACR	American College of Rheumatology
ACR20/50/70	20%/50%/70% improvement in tender and swollen joint counts and 20%/50%/70% improvement in 3 of the 5 ACR-core set measures
ADA	Anti-drug antibody
ADCC	Antibody-dependent cell mediated cytotoxicity
AE	Adverse event
ALT	Alanine transaminase
AMD	Age-related macular degeneration
AP	Alkaline phosphatase
aPTT	Activated partial thromboplastin time
AST	Aspartate transaminase
AUC	Area under the curve
AUC 0-∞	Area under plasma (serum) concentration-versus-time curve (time zero to infinity)
AUC 0-t	Area under the plasma (serum) concentration-versus-time curve (time zero to time of last quantifiable concentration)
BAL	Bronchoalveolar lavage
βhCG	Beta-subunit human chorionic gonadotropin
BCG	Bacillus Calmette-Guérin
BFI	Brief Fatigue Inventory
BMI	Body mass index
BNP	B-type natriuretic peptide
CDAI	Clinical disease activity index
CD20	Cluster of differentiation antigen 20
CDC	Complement-dependent cytotoxicity
CIA	Collagen-induced arthritis
COX	Cyclo-oxygenase
CPK	Creatine phosphokinase
CRO	Contract Research Organization
CRP	C-reactive protein
CTC	Common terminology criteria
CYP	Cytochrome P
CXR	Chest X-ray (radiograph)
DAS28	Disease activity score for 28 different joints
DAS28(CRP)	Disease activity score for 28 different joints with CRP value
DAS28(ESR)	Disease activity score for 28 different joints with ESR value
D LCO	Diffusing capacity of the lung for carbon monoxide
DNA	Deoxyribonucleic acid
DMARD	Disease modifying antirheumatic drugs

DRC	Data Review Committee
DRE	Disease-related event
ECG	Electrocardiogram
eCRF	Electronic case report form
EOW	Every other week
ESR	Erythrocyte sedimentation rate
EULAR	European League against Rheumatism
EW	Early withdrawal
FACIT	Functional assessment of chronic illness therapy
FEV1	Forced expiratory volume in one second
FRP	Females of reproductive potential
FSH	Follicle-stimulating hormone
FVC	Forced vital capacity
GGH	Gamma-glutamyl transpeptidase
GM-CSF	Granulocyte-macrophage colony stimulating factor
GM-CSFR $\alpha$	Granulocyte-macrophage colony stimulating factor receptor $\alpha$ chain
GSK	GlaxoSmithKline
h	Hour
HAQ-DI	Health Assessment Questionnaire Disability Index
HDL	High-density lipoprotein
HLA	Human leukocyte antigen
HRCT	High-resolution computed tomography
HRT	Hormone replacement therapy
HV	Healthy volunteer
IA	Intra-articular
IB	Investigator's brochure
IC50	The half maximal inhibitory concentration
ICH	International Conference on Harmonization
IFN $\gamma$	Interferon gamma
IL-1 $\beta$	Interleukin 1 beta
IL-4	Interleukin 4
IL-6	Interleukin 6
IL-10	Interleukin 10
IL-13	Interleukin 13
IL-17	Interleukin 17
IL-22	Interleukin 22
IL-23	Interleukin 23
IM	Intramuscular
IMP	Investigational medicinal product
INN	International non-proprietary name
INR	International normalized ratio
IP	Investigational product
IR	Inadequate response
IRTS	Interactive response technology system
ITT	Intent to Treat
IU	International units

IV	Intravenous
kDa	Kilodalton
kg	Kilogram
KL-6	Krebs von den Lungen-6
L	Litre
LDH	Lactate dehydrogenase
LDL	Low-density lipoprotein
LFT	Lung function test
mAb	Monoclonal antibody
MCV	Mean cell volume
MCH	Mean corpuscular hemoglobin
MCHC	Mean corpuscular hemoglobin concentration
MedDRA	Medical dictionary for regulatory activities
mg	Milligram
mL	Milliliter
MMP-3	Matrix metalloproteinase 3
MSD	Mesoscale discovery
MSDS	Material safety data sheet
MSS	Modified Sharp score
MTX	Methotrexate
n.a.	Not applicable
n.d.	Not determined
ng	Nanogram
NOEL	No observed effect level
NOAEL	No observed adverse effect level
NSAID	Non-steroidal anti-inflammatory drug
OMERACT	Outcome Measures in Rheumatology
PAP	Pulmonary alveolar proteinosis
PBMC	Peripheral blood mononuclear cells
PD	Pharmacodynamic
PFT	Pulmonary function test
PtGA	Patient's Global Assessment of Arthritis
PhGA	Physician's Global Assessment of Arthritis
PK	Pharmacokinetics
pM	Picomolar
PT	Prothrombin Time
PTS-DMPK	Platform Technologies and Science - Drug Metabolism and Pharmacokinetics
RA	Rheumatoid arthritis
RAP	Reporting and analysis plan
RF	Rheumatoid factor
SC	Subcutaneous
SAA	Serum amyloid A
SAE	Serious adverse event
SDAI	Simple disease activity index
SJC	Swollen joint count

SF-36	Short form (36)
SOP	Standard operating procedure
SP-D	Surfactant D
SRM	Study Reference Manual
SRT	Safety Review Team
t½	Elimination half-life
TARC	Thymus and activation regulated cytokine
TB	Mycobacterium tuberculosis
TEAE	Treatment emergent adverse event
TJC	Tender joint count
TNFα	Tumor necrosis factor alpha
TST	Tuberculin skin test
ULN	Upper limit of normal

### Trademark Information

Trademarks of the GlaxoSmithKline group of companies	Trademarks not owned by the GlaxoSmithKline group of companies
NONE	MEDdra MONOLIX NONMEM VII SF-36v2

## 12.2. Appendix 12.2 - Contraception eligibility criteria for female and male subjects

### 12.2.1. Females

A female subject is eligible to participate if she is not pregnant (as confirmed by a negative serum human chorionic gonadotropin [ $\beta$ hCG] test), not lactating, and at least one of the following conditions applies:

a. Non-reproductive potential defined as:

- Pre-menopausal females with one of the following:
  - Documented tubal ligation.
  - Documented hysteroscopic tubal occlusion procedure with follow-up confirmation of bilateral tubal occlusion.
  - Hysterectomy.
  - Documented bilateral oophorectomy.
- Postmenopausal defined as 12 months of spontaneous amenorrhea [in questionable cases a blood sample with simultaneous follicle-stimulating hormone (FSH) and estradiol levels consistent with menopause (refer to laboratory reference ranges for confirmatory levels)]. Females on hormone replacement therapy (HRT) and whose menopausal status is in doubt will be required to use one of the highly effective contraception methods if they wish to continue their HRT during the study. Otherwise, they must discontinue HRT to allow confirmation of post-menopausal status prior to study enrolment.

b. Reproductive potential and agrees to follow one of the options listed below in the **Modified List of Highly Effective Methods for Avoiding Pregnancy in Females of Reproductive Potential (FRP)** requirements from 30 days prior to the first dose of study medication and until 12 weeks after the last dose of study medication and completion of the follow-up visit. **If using hormonal contraceptives, including oral, injections, implants, and patches, a secondary method of contraception must be used.**

The investigator is responsible for ensuring that subjects understand how to properly use these methods of contraception.

#### **Modified List of Highly Effective Methods for Avoiding Pregnancy in Females of Reproductive Potential (FRP)**

This list does not apply to FRP with same sex partners or for subjects who are and will continue to be abstinent from penile-vaginal intercourse on a long term and persistent basis, when this is their preferred and usual lifestyle. Periodic abstinence (e.g. calendar, ovulation, symptothermal, post-ovulation methods) and withdrawal are not acceptable methods of contraception.

- Contraceptive subdermal implant.

- Intrauterine device or intrauterine system.
- Combined estrogen and progestogen oral contraceptive [Hatcher, 2011].
- Injectable progestogen [Hatcher, 2011].
- Contraceptive vaginal ring [Hatcher, 2011].
- Percutaneous contraceptive patches [Hatcher, 2011].
- Male partner sterilization with documentation of azoospermia prior to the female subject's entry into the study, and this male is the sole partner for that subject [Hatcher, 2011]. The documentation on male sterility can come from the site personnel's review of subject's medical records, medical examination and/or semen analysis, or medical history interview provided by her or her partner.

These allowed methods of contraception are only effective when used consistently, correctly and in accordance with the product label. If using hormonal contraceptives, including oral, injections, implants, and patches, a secondary method of contraception must be used. The investigator is responsible for ensuring that subjects understand how to properly use these methods of contraception.

#### **12.2.2. Males**

Male subjects with female partners of child bearing potential must comply with the following contraception requirements from the time of first dose of study medication until 12 weeks after the last dose of study medication.

- a. Vasectomy with documentation of azoospermia. The documentation on male sterility can come from the site personnel's review of subject's medical records, medical examination and/or semen analysis, or medical history interview.
- b. Male condom plus partner use of one of the contraceptive options below:
  - Contraceptive subdermal implant.
  - Intrauterine device or intrauterine system.
  - Combined estrogen and progestogen oral contraceptive [Hatcher, 2011].
  - Injectable progestogen [Hatcher, 2011].
  - Contraceptive vaginal ring [Hatcher, 2011].
  - Percutaneous contraceptive patches [Hatcher, 2011].

These allowed methods of contraception are only effective when used consistently, correctly and in accordance with the product label. The investigator is responsible for ensuring that subjects understand how to properly use these methods of contraception.

Male subjects should not donate sperm during the course of the study and should follow local guidelines thereafter.

### 12.3. Appendix 12.3 - Liver Safety Required Actions and Follow-up Assessments

#### Liver chemistry stopping criteria and required follow up assessments

Liver Chemistry Stopping Criteria – Liver Stopping Event	
ALT-absolute	ALT $\geq$ 5xULN
ALT Increase	ALT $\geq$ 3xULN persists for $\geq$ 4 weeks
Bilirubin	ALT $\geq$ 3xULN and bilirubin $\geq$ 2xULN ( $>35\%$ direct bilirubin)
INR^2	ALT $\geq$ 3xULN and INR $>1.5$ , if INR measured
Cannot Monitor	ALT $\geq$ 3xULN and cannot be monitored weekly for 4 weeks
Symptomatic	ALT $\geq$ 3xULN associated with symptoms (new or worsening) believed to be related to liver injury or hypersensitivity
Required Actions and Follow up Assessments following ANY Liver Stopping Event	
Actions	Follow Up Assessments

 
• Immediately discontinue study treatment
 
• Report the event to GSK within 24 hours
 
• Complete the liver event CRF and complete an SAE data collection tool if the event also meets the criteria for an SAE
 
• Perform liver event follow up assessments
 
• Monitor the subject until liver chemistries resolve, stabilize, or return to within baseline (see MONITORING below)
 
• Do not restart/rechallenge subject with study treatment unless allowed per protocol and GSK Medical Governance approval is granted.
 
• If restart/rechallenge not allowed per protocol or not granted, permanently discontinue study treatment and may continue subject in the study for any protocol specified follow up assessments
 
 
MONITORING: For bilirubin or INR criteria:
	
 
• Viral hepatitis serology
 
• Blood sample for pharmacokinetic (PK) analysis, obtained less than 12 weeks after last dose
 
• Serum creatine phosphokinase (CPK) and lactate dehydrogenase (LDH).
 
• Fractionate bilirubin, if total bilirubin <math>\geq</math>2xULN
 
• Obtain complete blood count with differential to assess eosinophilia
 
• Record the appearance or worsening of clinical symptoms of liver injury, or hypersensitivity, on the AE report form
 
• Record use of concomitant medications on the concomitant medications report form including acetaminophen, herbal remedies, other over the counter medications.
 
• Record alcohol use on the liver event alcohol intake case report form
 


 
Repeat liver chemistries (include ALT, AST, alkaline phosphatase, bilirubin) and perform liver event follow up assessments within 24 hrs
 
Monitor subjects twice weekly until liver chemistries resolve, stabilize or return to within baseline
 
A specialist or hepatology consultation is recommended
 
 
For All other criteria:
 
 
Repeat liver chemistries (include ALT, AST, alkaline phosphatase, bilirubin) and perform liver event follow up assessments within 24-72 hrs
 
Monitor subjects weekly until liver chemistries resolve, stabilize or return to within baseline
 
	
For bilirubin or INR criteria:
 
 
Anti-nuclear antibody, anti-smooth muscle antibody, Type 1 anti-liver kidney microsomal antibodies, and quantitative total immunoglobulin G (IgG or gamma globulins).
 
Serum acetaminophen adduct HPLC assay (quantifies potential acetaminophen contribution to liver injury in subjects with definite or likely acetaminophen use in the preceding week [James, 2009]).
 
Liver imaging (ultrasound, magnetic resonance, or computerised tomography) and/or liver biopsy to evaluate liver disease: complete Liver Imaging and/or Liver Biopsy CRF forms.
 

--	---

1. Serum bilirubin fractionation should be performed if testing is available. If serum bilirubin fractionation is not immediately available, discontinue study treatment for that subject if ALT  $\geq 3 \times \text{ULN}$  and bilirubin  $\geq 2 \times \text{ULN}$ . Additionally, if serum bilirubin fractionation testing is unavailable, **record presence of detectable urinary bilirubin on dipstick**, indicating direct bilirubin elevations and suggesting liver injury.
2. All events of ALT  $\geq 3 \times \text{ULN}$  and bilirubin  $\geq 2 \times \text{ULN}$  ( $>35\%$  direct bilirubin) or ALT  $\geq 3 \times \text{ULN}$  and INR  $>1.5$ , if INR measured which may indicate severe liver injury (possible 'H's Law'), **must be reported as an SAE (excluding studies of hepatic impairment or cirrhosis)**; INR measurement is not required and the threshold value stated will not apply to subjects receiving anticoagulants
3. New or worsening symptoms believed to be related to liver injury (such as fatigue, nausea, vomiting, right upper quadrant pain or tenderness, or jaundice) or believed to be related to hypersensitivity (such as fever, rash or eosinophilia)
4. Includes: Hepatitis A IgM antibody; Hepatitis B surface antigen and Hepatitis B Core Antibody (IgM); Hepatitis C RNA; Cytomegalovirus IgM antibody; Epstein-Barr viral capsid antigen IgM antibody (or if unavailable, obtain heterophile antibody or monospot testing); Hepatitis E IgM antibody
5. PK sample may not be required for subjects known to be receiving placebo or non-GSK comparator treatments.) Record the date/time of the PK blood sample draw and the date/time of the last dose of study treatment prior to blood sample draw on the CRF. If the date or time of the last dose is unclear, provide the subject's best approximation. If the date/time of the last dose cannot be approximated OR a PK sample cannot be collected in the time period indicated above, do not obtain a PK sample. Instructions for sample handling and shipping are in the SRM.

## Liver chemistry increased monitoring criteria with continued therapy

Liver Chemistry Increased Monitoring Criteria – Liver Monitoring Event	
Criteria	Actions
ALT $\geq$ 3xULN and <5xULN and bilirubin <2xULN, without symptoms believed to be related to liver injury or hypersensitivity, and who can be monitored weekly for 4 weeks	
 
Notify the Medical Monitor within 24 hours of learning of the abnormality to discuss subject safety.
 
Subject can continue study treatment
 
Subject must return weekly for repeat liver chemistries (ALT, AST, alkaline phosphatase, bilirubin) until they resolve, stabilise or return to within baseline
 
If at any time subject meets the liver chemistry stopping criteria, proceed as described above
 
If, after 4 weeks of monitoring, ALT <3xULN and bilirubin <2xULN, monitor subjects twice monthly until liver chemistries normalize or return to within baseline.
 

## 12.4. Appendix 12.4 - Definition of and Procedures for Recording, Evaluating, Follow-Up and Reporting of Adverse Events

### 12.4.1. Definition of Adverse Events

#### Adverse Event Definition:

- An AE is any untoward medical occurrence in a patient or clinical investigation subject, temporally associated with the use of a medicinal product, whether or not considered related to the medicinal product.
- NOTE: An AE can therefore be any unfavorable and unintended sign (including an abnormal laboratory finding), symptom, or disease (new or exacerbated) temporally associated with the use of a medicinal product.

#### Events meeting AE definition include:

- Any abnormal laboratory test results (hematology, clinical chemistry, or urinalysis) or other safety assessments (*e.g.*, ECGs, radiological scans, vital signs measurements), including those that worsen from baseline, and felt to be clinically significant in the medical and scientific judgement of the investigator.
- Exacerbation of a chronic or intermittent pre-existing condition including either an increase in frequency and/or intensity of the condition.
- New conditions detected or diagnosed after study treatment administration even though it may have been present prior to the start of the study.
- Signs, symptoms, or the clinical sequelae of a suspected interaction.
- Signs, symptoms, or the clinical sequelae of a suspected overdose of either study treatment or a concomitant medication (overdose *per se* will not be reported as an AE/SAE unless this is an intentional overdose taken with possible suicidal/self-harming intent. This should be reported regardless of sequelae).
- "Lack of efficacy" or "failure of expected pharmacological action" *per se* will not be reported as an AE or SAE. However, the signs and symptoms and/or clinical sequelae resulting from lack of efficacy will be reported if they fulfil the definition of an AE or SAE.

#### Events NOT meeting definition of an AE include:

- Any clinically significant abnormal laboratory findings or other abnormal safety assessments which are associated with the underlying disease, unless judged by the investigator to be more severe than expected for the subject's condition.
- Signs and symptoms of RA disease activity, *e.g.* joint pain, swelling, erythema, warmth, and stiffness, or expected progression, should not be reported as AEs, unless in the investigator's opinion they are of greater intensity, frequency or duration than

expected for the individual subject.

- Medical or surgical procedure (e.g., endoscopy, appendectomy): the condition that leads to the procedure is an AE.
- Situations where an untoward medical occurrence did not occur (social and/or convenience admission to a hospital).
- Anticipated day-to-day fluctuations of pre-existing disease(s) or condition(s) present or detected at the start of the study that do not worsen.

#### **12.4.2. Definition of Serious Adverse Events**

If an event is not an AE per definition above, then it cannot be an SAE even if serious conditions are met (e.g., hospitalization for signs/symptoms of the disease under study, death due to progression of disease, etc).

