#### **7.4.6.1. Disease-Related Events and/or Disease-Related Outcomes Not Qualifying as SAEs**

The following have been specified as disease-related events (DREs) for the study:

- Events related to exacerbation of articular/peri-articular manifestations of RA, will not be reported as AEs, and will be recorded in the DRE eCRF.
- Events related to the articular/peri-articular flare up of the disease, and that require hospitalization, will not be reported as SAEs. However, such events must still be recorded in the DRE eCRF.

These DREs will be monitored by an SRT on a routine basis.

NOTE: However, if either of the following conditions apply, then the event must be recorded and reported as an SAE (instead of a DRE):

- The event is, in the investigator's opinion, of greater intensity, frequency, or duration than expected for the individual subject.

OR

- The investigator considers that there is a reasonable possibility that the event was related to treatment with the investigational product.

New onset or worsening of extra-articular manifestations of RA should be reported as AEs/SAEs.

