#### 4.10.3 Deaths and Serious Adverse Events

The following summaries will be provided by actual treatment group at the time of the event:

- Number and percentage of subjects reporting a serious AE by SOC and PT
- Number and percentage of subjects reporting a serious AE by relationship to study treatment
- Number and percentage of AEs leading to death by relationship to study medication
- Exposure-adjusted (patient years) serious adverse events by treatment group, where the total number of subjects for each column includes all subjects who took the dose at least once during the study. The exposure-adjusted rate divides the total number of serious AEs attributed to each dose by duration of exposure (in years) to that dose. The duration for subjects who complete the study on their randomised dose is (date of last dose – date of first dose + 1). For subjects who escape, duration is based on treatment periods defined in Section 4.2.

The following listings will be provided:

- A by-subject listing of all Serious AEs
- A by-subject listing of all AEs leading to discontinuation of study treatment
- A by-subject listing of all Serious AEs leading to death

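### A hospitalised RA flare of expected intensity that may be drug-related must be an SAE under Protocol 7.4.6.1 and cannot be one under Appendix 12.4

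*Protocol*

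**What the plan says.** Protocol 7.4.4 names Appendix 12.4 as the place where AEs and SAEs are defined.

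- **Appendix 12.4.1, general definition.** An AE is any untoward occurrence, "whether or not considered related to the medicinal product". Relatedness plays no part in AE status.
- **Appendix 12.4.1, exclusions.** "Signs and symptoms of RA disease activity, *e.g.* joint pain, swelling, erythema, warmth, and stiffness, or expected progression, should not be reported as AEs". The sentence carries one exception, for events beyond what was expected for that subject: they "should not be reported as AEs, unless in the investigator's opinion they are of greater intensity, frequency or duration than" expected.
- **Appendix 12.4.2.** "If an event is not an AE per definition above, then it cannot be an SAE even if serious conditions are met". The examples given are "hospitalization for signs/symptoms of the disease under study, death due to progression of disease".
- **Section 7.4.6.1.** Articular or peri-articular flares go on the DRE eCRF. By default they are not AEs, nor SAEs if hospitalised. The event must instead be reported as an SAE if either of two conditions applies. One is the worse-than-expected condition of 12.4.1. The other is: "The investigator considers that there is a reasonable possibility that the event was related to treatment with the investigational product". The section adds: "New onset or worsening of extra-articular manifestations of RA should be reported as AEs/SAEs".
- **Deaths.** Protocol 7.4.4.4 requires the Death eCRF for every death, SAE or not. SAP 4.10.2 and 4.10.3 summarise AEs leading to death and provide "A by-subject listing of all Serious AEs leading to death".

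**The concern.** Relatedness alone makes a flare a mandatory SAE in 7.4.6.1. That condition is missing from the appendix that supplies the definitions, and the appendix closes the gap with an explicit bar. Two investigators could each follow the protocol and classify the same event differently.

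The affected events are serious and suspected to be drug-related, which is the kind that prompt reporting is meant to catch. SAE incidence is also a major secondary safety endpoint, so the classification reaches the study's reported results as well as its pharmacovigilance.

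**Working it through.** No arithmetic applies. The check sets the two sets of rules side by side, by type of event.

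| Event | Section 7.4.6.1 | Appendix 12.4.1 and 12.4.2 | Result |
|---|---|---|---|
| Hospitalised articular flare, as expected, not thought related | DRE, not an SAE | Not an AE, so not an SAE | Agree |
| Hospitalised articular flare, worse than expected | SAE | AE by the exception; SAE by hospitalisation | Agree |
| Hospitalised articular flare, as expected, possibly drug-related | SAE, mandatory | Not an AE, so cannot be an SAE | **Contradict** |
| New or worsening extra-articular RA | AE, or SAE if serious | Not mentioned by name | Ambiguous |
| Death due to RA progression | Not mentioned | Not an SAE if not an AE | No direct conflict |

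**Third row.** The two conditions in 7.4.6.1 are alternatives, so suspected relatedness is enough without unusual severity. In 12.4.1 only unusual severity restores AE status. The general AE definition cannot supply the missing route, because it disregards causality. The event therefore falls under the bar in 12.4.2, whose first example is hospitalisation for the disease under study.

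**Consequences of the third row.**

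| Step | Treated as an SAE | Treated as a DRE |
|---|---|---|
| Report to the sponsor (Protocol 7.4.4.1) | Within 24 hours | SAE clock does not apply |
| Investigator safety report (Protocol 7.4.6.2) | Possible, if also unexpected | Not triggered |
| Study tables (SAP 4.10.3, 4.10.4) | SAE tables, including by relationship | DRE summary and listing only |
| Data review committee (SAP 4.10.11.1) | In the SAE summary | No DRE summary among the listed outputs |
| Safety review team (Protocol 4.7.3, 7.4.6.1) | Reviewed blinded | Reviewed blinded |

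**Fourth row.** The RA signs that 12.4.1 gives as examples are articular, and 12.4.1 counts exacerbation of a pre-existing condition as an AE. It can therefore be read in line with 7.4.6.1. Two phrases leave room for doubt. One is the exclusion of expected progression. The other, also in 7.4.5, excludes abnormal safety assessments tied to the underlying disease unless more severe than expected.

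**Fifth row.** A death classed as progression of expected course can be a non-AE under 12.4.2. The Death eCRF would hold it, but the death outputs in SAP 4.10.2 and 4.10.3 are restricted to AEs and SAEs. It might appear as a withdrawal reason in the disposition outputs of SAP 4.4.1; the SAP does not say so.

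**The case against.** The best defence is that 7.4.6.1 is the specific, mandatory rule for these events, and a specific rule ordinarily prevails over a general definition. That is a sensible reading, but the protocol nowhere states it. Section 7.4.4 points to the appendix for the definitions, and the exclusion in 12.4.1 is itself written for RA rather than being generic text.

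It is also fair to say that DREs are not lost. They have their own eCRF and routine review by the safety review team. They are part of the monthly blinded data review (SAP 3.1.4) and have a summary and listing by actual treatment group. This limits the harm. It does not replace 24-hour reporting or put the event in the unblinded committee's listed outputs.

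Four stronger readings are tempting, and the documents do not support them.

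- **That 12.4.2 bars every disease-related hospitalisation or death from being an SAE.** The sentence is conditional on the AE definition, which admits events worse than expected. On ordinary hospitalised flares both sections have the same default.
- **That extra-articular disease must be an SAE under 7.4.6.1 and is excluded by the appendix.** The rule in 7.4.6.1 covers AEs and SAEs, so seriousness still decides, and the appendix does not clearly exclude these events.
- **That lung toxicity would drop out of view.** The contradiction concerns articular flares. Alveolar proteinosis, surfactant-related lung changes and persistent cough or dyspnoea are AEs of special interest (Protocol 7.4.6). SAP 4.10.5 and 4.10.9 report respiratory events and lung function, and the data review committee receives summaries of persistent cough, dyspnoea and DLCO decrease.
- **That an assumed rate of hospitalised flares among 210 subjects gives the number affected.** Such a figure would include unrelated and worse-than-expected flares, on which the sections agree.

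**Conclusion.** The SAE rule is wrong as written: it contradicts itself on one class of event. That class is an articular or peri-articular flare of expected intensity that meets a serious criterion and that the investigator considers possibly related to investigational product. Each such event is an SAE under 7.4.6.1 and cannot be one under 12.4.1 and 12.4.2.

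The documents give no flare, hospitalisation or relatedness rates, so the number of events is unknown and I give no range. The conclusion rests on the text alone and assumes that no document outside the protocol and SAP sets an order of precedence. The statement about the data review committee rests on the outputs listed in SAP 4.10.11.1; the separate output shells were not available.

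Two related matters are lesser. The handling of extra-articular manifestations in 12.4.1 is an ambiguity. The lack of an all-deaths output is a gap in the SAP and not a conflict with 7.4.6.1, which does not mention death.

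**What to change.** Reconcile the passages in one edit of the appendix:

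1. In 12.4.1, add suspected relation to investigational product as a second exception to the exclusion of RA signs, symptoms and expected progression, matching 7.4.6.1.
2. In 12.4.2, make the sentence barring non-AEs subject to 7.4.6.1.
3. In 12.4.1, state that extra-articular manifestations are handled as in 7.4.6.1.

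The same edit could settle a smaller mismatch: 7.4.6.1 turns a DRE that meets either condition into an SAE without asking for a serious criterion, whereas 12.4.2 requires one.

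Separately, add to SAP 4.10.3 a listing of all deaths from the Death eCRF, whatever their AE status.

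The cost is a few clauses in the appendix and one listing from data already collected. Design, treatment and sample size do not change. The SAE count may rise slightly where sites would have followed the appendix.
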